Maxillary lateral incisor extrusion is one of the least effective movements with clear aligners. Orthodontists and general dentists using their expertise can design clear aligner attachments how they see fit for the particular tooth movement they are trying to achieve. Currently there is no evidence in the literature that compares the efficacy of different attachment designs for maxillary lateral extrusion. There is however, anecdotal evidence based on clinician experience regarding which attachment is more efficacious different experts tout different designs. This study will serve as a guide for clinicians to design the best attachment for the most effective and predictable extrusion of the maxillary lateral incisor. More predictable and effective lateral extrusion will limit the need for midcourse intervention for patients and that will result in less appliances and treatment time.

5. * Describe any potential for direct benefits to participants in this study:

Although all attachments are known to be somewhat effective in lateral incisor extrusion, patients in one arm of the study may benefit more from the use of specific type of attachment that was randomly assigned to that group.

6. Upload a supporting citation list if applicable:

ID: HM20021396

View: SF2 - Study Population

Study Population

1. * Provide the maximum number of individuals that

1. May participate in any study interaction or intervention (Including screening, consenting, and study activities)

AND/OR

2. You obtain any data/specimens about (regardless of identifiability)

at VCU and at other sites under the VCU IRB's oversight. See the help text for additional guidance.
80

2. If this is a multi-Center Project, what is the maximum anticipated number of subjects across all sites?

The maximum anticipated number of subjects is 80.

3. * Provide justification for the sample size by explaining how you arrived at the expected number of participants and why this number is adequate for answering the research questions:

A power analysis was used to determine the need for 20 maxillary lateral incisors for each of the four attachment design groups.

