Based on data from prior publications, the common standard deviation for extrusion was assumed to be 1.25. When the sample size is 15, a one-way repeated measures analysis of variance with a 0.05 significance level will have 80% power to detect a difference in means across the 4 groups of the repeated measures factor characterized by an effect size of 0.199 (based on a Variance of means, $V = \frac{(\sigma^2 - \rho^2)}{M}$, of 0.156, a standard deviation at each level of 1.25, and a between level correlation, ρ , of 0.5).

Increasing the sample size to 20 per group would have power to detect an effect size of 0.146 and variance of means of 0.114. These estimates reflect small effect sizes 15 and therefore would be able to detect clinically meaningful differences in the extrusion of the 4 attachments. Sample size calculations estimated with nQuery v8.5.2 (Statistical Solutions Ltd 2020).

4. * List the study inclusion criteria:

- (1) Patients 16 years or older to be treated with either Comprehensive Invisalign or Invisalign Teen,
- (2) Maxillary lateral incisor requiring 0.3 mm or more extrusion (as determined by ClinCheck),
- (3) Maxillary arch with less than 6 mm of crowding or spacing,
- (4) All teeth present and fully erupted (excluding third molars).

5. * List the study exclusion criteria:

- (1) Presence of anterior crossbite
- (2) Any missing teeth in the maxillary arch
- (3) Treatment plan includes surgery or extraction of any maxillary teeth,
- (4) Maxillary lateral incisors with pathology or large restorations (crowns)
- (5) Maxillary lateral incisors have a less than 0.3 mm of extrusion prescribed in the Tooth Movement Table on the Invisalign ClinCheck

6. * Will individuals with limited English proficiency be included in or excluded from this research?

Included

- Excluded - safety concerns if participants are unable to communicate with the study team
- Excluded - instruments/measures only validated in English
- Excluded - no prospect of direct benefit to individual participants
- Excluded - minimal risk study
- Excluded - lack of budget/resources for translation and interpretation [provide an explanation in next question]
- Excluded - other reason [provide an explanation in next question]

7. Justify the inclusion and exclusion criteria if you are either targeting, or excluding, a particular segment of the population / community. Provide a description of the group/organization/community and provide a rationale.

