During the scheduled appointment for the delivery of aligners, the patients will be instructed on how to properly place and remove aligners and their maintenance. Patients will be instructed to wear each aligner for a minimum of 22 hours a day for 7 days. Participants will verbally confirm compliance at each appointment. At the end of a series of 20-25 aligners, another intraoral scan will be taken and sent to Align Technologies to determine the final positions of the teeth. Comparison of initial and final positions (using Geomagic software) will be done to assess the efficacy of different types of attachments in lateral incisor extrusion.

Once the teeth are in desired positions, the treating orthodontist will remove the attachment (<6 months).

3.

Research related interventions include:

- a. random assignment of the specific type of attachment on lateral incisor;
- b. treating orthodontist placing the corresponding order in the prescription with Align Technology;
- c. delivery of attachments and aligners to the study participants
- d. Superimposition of final and initial positions of lateral incisors: Two superimpositions will be completed. The pretreatment model will be superimposed with the predicted final model to establish the predicted movement of the maxillary lateral incisors. The pretreatment model will be superimposed with the posttreatment model to establish the actual movement of the maxillary lateral incisor. The actual and predicted movement values will be calculated by the GeoMagic software. The amount of extrusion for the lateral incisors will be analyzed in increments of 0.1 mm.

Sample size: 80 maxillary lateral incisors with at least 20 teeth per study group. Randomization will occur at the level of individual lateral incisor tooth.

Study Duration: Patients will be evaluated only after the first series of aligners (20-25). Each set of aligners would be worn for a week and the study would span 20 - 25 weeks.

7. * The IRB only reviews research activities, so indicate which of the study activities are:

- **Being performed exclusively for research purposes (i.e. they would not otherwise be done apart from this study) VERSUS.**
- **Alterations of routine activities/procedures (e.g. the study is altering the timing, frequency, method, location, amount, etc.) VERSUS.**

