Costs to Participants

1. * Select all categories of costs that participants or their insurance companies will be responsible for:

- Participants will have no costs associated with this study
- Study related procedures that would be done under standard of care
- Study related procedures not associated with standard of care
- Administration of drugs / devices
- Study drugs or devices
- Other

ID: HM20021396

View: SF2 - Compensation

Compensation

1. * Describe any compensation that will be provided including:
 1. total monetary amount
 2. type (e.g., gift card, cash, check, merchandise, drawing, extra class credit)
 3. how it will be disbursed

Every lateral incisor that requires extrusion and qualifies for the study will be compensated with a \$50 gift card. The compensation will be distributed to study participants in person when they complete the second intraoral scan at the end of their initial series of clear aligners. Since there are two lateral incisors, a study participant's potential compensation can be \$100 if both their lateral incisors qualify for the study.

2. If compensation will be pro-rated, explain the payment schedule.
Compensation will not be pro-rated.

3. * Will Social Security Numbers be collected for compensation purposes only?

Yes
 No

ID: HM20021396

View: SF2 - Research Plan Complete

Research Complete

Protocol Progress:

- ? INITIAL SETUP
- ? BACKGROUND, RATIONALE & GOALS
- ? RESEARCH PLAN
- ? CONSENT PLAN
- ? RISKS, PRIVACY & CONFIDENTIALITY
- ? POPULATIONS WITH SPECIAL CONSIDERATIONS
- ? INSTITUTIONAL REQUIREMENTS
- ? DOCUMENTS

Click Continue below to go to the next section

ID: HM20021396

View: SF2 - Consent Process

Consent Process

1. * List all consent groups:

Group Types	Waivers	Roles	Roles - Other	Consent	Coercion	Decision	Re-Consent

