The study is a 4-arm randomized trial. Subjects will be screened for eligibility based on inclusion/ exclusion criteria. Once informed consent is obtained, the participants will be randomly assigned to one of the four attachment designs. The biostatistician on the study team ([name]) will generate random sequence using a computer. The randomization will be in block of 4 and the list will be provided to the study team.

All study participants will be assigned a unique identifier (4 digit code) generated by the study team based on order of enrollment and whether they received horizontal, incisally bevelled, gingivally bevelled or optimized attachments. This key that links code to the patient will be stored in the PI's office computer that has restricted access (only to study personnel). The key will be destroyed when the all participants complete their second scan (data collection is complete).

All data records used for analysis will have this assigned code without any identifying information. This will minimize the amount of recontacting needed for children who turn 18 during data analysis stage.

ID: HM20021396

View: SF2 - Data Retention

Data Retention

1. * **Select all of the ways that individually identifiable information obtained during pre-screening and/or screening will be handled for individuals who DO NOT qualify for the study:**
 - Immediately destroy the information and identifiers (no data collected)
 - Immediately destroy the identifiers connected with the data (anonymization)
 - Store until the end of study & then destroy
 - Use as "screening failure" data by members of the study team
 - Provide to others outside of the research team (with the participant's permission)
 - Request permission from participant to maintain and use the identifiable information
 - Other
 - N/A - study does not require screening procedures**
2. * **Will participants be able to withdraw their data (paper, electronic, or specimens) from the study (e.g. ask that it be destroyed or returned) if they no longer wish to participate? (FDA-regulated studies should select No - see help text)**
 - Yes
 - No**
3. * **What will happen to the research materials (e.g. data, specimens, documents, etc.) when the research has been completed?**
 - Stored indefinitely with identifiers removed
 - Stored indefinitely with identifiers attached

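### The 80% power is for a design in which every subject receives all four attachments; the planned 80 teeth give about 32% to 69% for the same effect

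*Combined protocol and SAP*

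**What the plan says.** Study Population, Q3 opens with the conclusion: "A power analysis was used to determine the need for 20 maxillary lateral incisors for each of the four attachment design groups". The basis is that, with a sample size of 15, a "one-way repeated measures analysis of variance with a 0.05 significance level will have 80% power to detect a difference in means" across four levels of the repeated measures factor. The inputs are an SD of 1.25 at each level, a between-level correlation of 0.5, a variance of means of 0.156 and an effect size of 0.199. It continues: "Increasing the sample size to 20 per group would have power to detect an effect size of 0.146 and variance of means of 0.114". It then concludes: "These estimates reflect small effect sizes 15 and therefore would be able to detect clinically meaningful differences in the extrusion of the 4 attachments".

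The design is described elsewhere. Study Procedures, Q6 states "Sample size: 80 maxillary lateral incisors with at least 20 teeth per study group" and "Randomization will occur at the level of individual lateral incisor tooth". Compensation, Q1 allows a patient two payments "if both their lateral incisors qualify for the study", so a patient has one or two study teeth. Data Confidentiality and Storage, Q9 calls the study a four-arm randomized trial and says that "the participants will be randomly assigned to one of the four attachment designs".

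**The concern.** A one-way repeated measures ANOVA with four levels needs four correlated measurements per subject, one under each attachment. Its gain in power comes from removing between-subject variation from every comparison. No section describes a tooth or a patient receiving all four designs. A patient can supply at most two of the four levels, only if both lateral incisors qualify, and only if the two teeth are given different designs. If both get the same design, the correlation reduces power instead.

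This paragraph is the only justification for 20 teeth per group. If its power figure belongs to another design, a non-significant result could be read as evidence that the four attachments perform alike when the trial had a much lower chance of showing a difference. The trial is meant to support clinical recommendations on attachment choice, so that misreading matters.

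**Working it through.** **Inputs** (Study Population, Q3 and Study Procedures, Q6): SD 1.25, so SD² = 1.5625; ρ = 0.5; α = 0.05; four groups; variance of means V = 0.156 (n = 15) and V = 0.114 (n = 20); 80 teeth, 20 per group. Power is from the noncentral F distribution with noncentrality λ.

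**1. Reproducing the plan's figures.** Effect size = V / [SD²(1 − ρ)]; λ = n × 4 × effect size; df = 3 and 3(n − 1).

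- n = 15: 0.156 / 0.78125 = 0.1997 (stated 0.199); λ = 11.98; df 3, 42; power 80.0%.
- n = 20: 0.114 / 0.78125 = 0.1459 (stated 0.146); λ = 11.67; df 3, 57; power 80.0%.

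So n counts subjects measured under all four attachments, with error variance SD²(1 − ρ), half of SD². The text gives 80% explicitly only for n = 15; for n = 20 it is inferred from this match.

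**2. The same effects with 80 teeth, one design per tooth, ρ = 0.5 between a patient's two teeth.**

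- Independent teeth: λ = 80V / SD². For V = 0.114 this is 9.12 / 1.5625 = 5.84.
- 40 patients, same design on both teeth: λ = 5.84 / (1 + ρ) = 3.89.
- 40 patients, teeth always on different designs in balanced pairs: λ = 5.84 × [(2/3)/(1 − ρ) + (1/3)/(1 + ρ)] = 5.84 × 1.556 = 9.08, equivalent to 20 × 1.556 = 31.1 independent teeth per arm.
- 40 patients, each tooth randomized independently: generalized least squares λ averaged over random allocations, 7.83.

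| Arrangement of the 80 teeth | Denominator df | Power, V = 0.114 | Power, V = 0.156 |
|---|---|---|---|
| Independent | 76 | 48.3% | 62.8% |
| 40 pairs, same design | 36 | 31.6% | 42.3% |
| 40 pairs, teeth randomized independently | 36 to 76 | 59–62% | 74–77% |
| 40 pairs, always different, balanced | 36 to 76 | 66–69% | 81–83% |

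With 20 bilateral and 40 unilateral patients, the three paired arrangements give 40%, 54–56% and 57–60% at V = 0.114. A simulation that estimates the variance components gives 59–62% for independent randomization of 40 pairs and 68–71% for always-different pairs, still below 80%.

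**3. What 80 teeth can detect with 80% power.** The best-to-worst difference runs from 2√V (two designs against two) to √(8V) (two extremes, two in the middle), in the units of the SD.

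- Independent teeth: V = 0.224; difference 0.95 to 1.34.
- 40 pairs, same design: V = 0.356; 1.19 to 1.69.
- 40 pairs, always different: V = 0.144 to 0.153; 0.76 to 1.11.

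Conversely, 80% power for V = 0.114 with independent teeth needs 39 per group, or 156 teeth.

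**4. The effect-size label.** The value 0.146 is a ratio of variances whose denominator is the within-subject error variance. On the between-group scale the same V gives 0.114 / 1.5625 = 0.073, or f = √0.073 = 0.27. A label attached to 0.146 does not transfer to the design being run. The text also names no difference that would count as clinically meaningful.

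**The case against.** The plan's arithmetic is correct for the model it names, and some use of within-patient correlation is reasonable because patients may contribute two teeth. That is credited above, and it recovers only part of the gain.

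The stronger objection is that the range rests on assumptions. The plan gives 0.5 as the correlation between levels of a model that does not apply, not as a left–right correlation. At ρ = 0.3, 40 pairs give 36% (same design) to 54–57% (always different) at V = 0.114; at ρ = 0.7 they give 28% to 86–88%. A high correlation with deliberately different designs could therefore exceed 80%. The sample is also not firmly capped at 80 teeth: Study Population allows up to 80 subjects and the group size is a minimum. Eighty bilateral patients (160 teeth) would have 62% with the same design on both teeth and over 90% otherwise. A fixed pairing placed exactly across the designs that differ can reach about 80% at ρ = 0.5, but the plan describes no such scheme.

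The 32% end also requires participant-level assignment, which conflicts with the explicit tooth-level statement in Study Procedures, Q6. Under tooth-level randomization without restriction, the range at ρ = 0.5 is about 48% (all unilateral) to 62% (all bilateral).

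These points stand as limits on the numbers. None makes the repeated-measures calculation applicable.

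**Conclusion.** The concern holds. The stated 80% power is correct for a four-level within-subject design and does not describe this trial. With the stated 80 teeth, SD 1.25 and V = 0.114, power is 48% for independent teeth. It runs from about 32% to 69% for 40 bilateral patients at an assumed within-patient correlation of 0.5, and no arrangement consistent with the plan's description reaches 80%. For the larger effect, V = 0.156, only the always-different arrangement does. The exact figure cannot be settled until the number of bilateral patients, the rule for a patient's two teeth and their correlation are fixed. The statements about small effect sizes and clinically meaningful differences are unsupported as written.

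**What to change.** Replace the repeated-measures statement in Study Population, Q3 with a calculation for the design being run. State the expected number of bilateral patients, the assignment rule for a patient's two teeth (reconciling Study Procedures, Q6 with Data Confidentiality and Storage, Q9), the within-patient correlation with a range, and the unit of the SD. Suggested wording:

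> With 20 teeth per arm, SD 1.25 [unit], α 0.05 and independent teeth, a four-group comparison has 80% power for a variance of means of 0.224 (f = 0.38; best-to-worst difference 0.95 to 1.34 in the units of the SD) and 48% power for 0.114. If 40 patients contribute two teeth each at an assumed within-patient correlation of 0.5, power for 0.114 ranges from about 32% (same design on both teeth) to 69% (always different designs), and the variance of means detectable with 80% power ranges from 0.36 to about 0.15.

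Delete the claims about small effect sizes and clinically meaningful differences, or name the difference regarded as meaningful and report the power for it.

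The cost is one reworded paragraph and a less favourable power statement, given as a range until the open points are fixed. The correction does not itself require a change in enrolment; whether the restated power is acceptable is for the investigators to judge.

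### The detectable effect sizes 0.199 and 0.146 are squared values and not small, so the sample-size section does not support its claim about clinically meaningful differences

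*Combined protocol and SAP*

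**What the plan says.** The sample-size justification is in Study Population, question 3. It assumes that "the common standard deviation for extrusion was assumed to be 1.25" (no unit is printed) and "a between level correlation, ρ , of 0.5". With 15 per group, "a one-way repeated measures analysis of variance with a 0.05 significance level will have 80% power" for a difference among four means "characterized by an effect size of 0.199", with a variance of means V = 0.156. It then goes to the planned size: "Increasing the sample size to 20 per group would have power to detect an effect size of 0.146 and variance of means of 0.114". The closing inference is: "These estimates reflect small effect sizes 15 and therefore would be able to detect clinically meaningful differences". The 15 inside that sentence looks like a citation number.

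Three other places matter for interpretation. Question 4 of the same section sets the entry criterion: "Maxillary lateral incisor requiring 0.3 mm or more extrusion (as determined by ClinCheck"). Study Procedures, question 6, plans 80 teeth with at least 20 per group and randomizes the individual tooth. The Compensation section allows for at most two qualifying teeth per participant.

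**The concern.** The sentence argues in two steps: the detectable effects are small, and therefore differences that matter clinically can be detected. If the label is wrong, the second step needs another basis, such as a stated target difference between designs. The protocol gives none.

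This is the sentence that ties the number of teeth to clinical meaning, in answer to a form question that asks why the number is adequate. The trial aims to give clinicians recommendations on which attachment to plan. If its sensitivity is overstated, a non-significant result is easily taken to mean that the four designs are interchangeable, when differences of several tenths of a millimetre would often have been missed.

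**Working it through.** **Inputs** (all from Study Population, question 3): M = 4 levels, α = 0.05, SD = 1.25, ρ = 0.5; V = 0.156 with effect size 0.199 at n = 15; V = 0.114 with effect size 0.146 at n = 20. Power of 80% is stated for n = 15 and taken to be the same for n = 20. The SD is assumed to be in mm.

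**1. Which scale are the effect sizes on?** The within-subject error variance is SD²(1 − ρ) = 1.5625 × 0.5 = 0.78125.
- n = 15: 0.156 / 0.78125 = 0.1997 (stated 0.199)
- n = 20: 0.114 / 0.78125 = 0.1459 (stated 0.146)

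A variance divided by a variance is f-squared.

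**2. Does the stated power reproduce?** Use the noncentral F with df1 = M − 1 = 3, df2 = (M − 1)(n − 1), and noncentrality n × M × f².

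| n | df2 | Power if the value is f² | Power if the value is f |
|---|---|---|---|
| 15 | 42 | 79.9% | 20.6% |
| 20 | 57 | 80.0% | 16.0% |

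Only the squared reading agrees with the plan's 80%. Read as f, the values would need 71 and 130 per group. The plan's arithmetic is sound; the label is not.

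**3. Convert to f.**
- Error-SD scale: √0.199 = 0.45 and √0.146 = 0.38
- Full-SD scale, √V / 1.25: √0.156 / 1.25 = 0.32 and √0.114 / 1.25 = 0.27

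The usual cut-offs for f are 0.10 (small), 0.25 (medium) and 0.40 (large). This is a general convention and is not in the protocol. The values run from medium to large, depending on the scale. At n = 20 under the plan's model, power for f = 0.10 is 10% on the error-SD scale and 15% on the full-SD scale; for f = 0.25 it is 41% and 73%.

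**4. Convert to millimetres.** For four means with variance V, the best-to-worst spread is smallest when two designs differ from the other two (2√V). It is largest when one is high, one is low and two lie in the middle (√(8V)).

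| Setting | V at 80% power | 2√V | √(8V) |
|---|---|---|---|
| Repeated measures, n = 15 | 0.156 | 0.79 mm | 1.12 mm |
| Repeated measures, n = 20 | 0.114 | 0.68 mm | 0.95 mm |
| Independent groups, n = 20 | 0.224 | 0.95 mm | 1.34 mm |

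The last row uses df2 = 4(n − 1) = 76 and noncentrality 4n × V/SD². Power is 80% at V/SD² = 0.1435, so V = 0.1435 × 1.5625 = 0.224. At the plan's V = 0.114, the independent-groups analysis has 48% power.

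**5. Smaller spreads, n = 20.** Each range runs from the least to the most favourable pattern of means.

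| Best-to-worst spread | Repeated measures | Independent groups |
|---|---|---|
| 0.3 mm | 12–20% | 8–12% |
| 0.5 mm | 27–52% | 15–28% |

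**The case against.** Several objections have force.

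- **The size label depends on the scale and on an outside convention.** Against the full SD the values are medium, and the cut-offs are not in the protocol. The source apparently cited as 15 cannot be seen here. This rules out calling the effects simply large. It does not restore *small*, which fits only if a squared value is read against the benchmarks for f. The gap in the inference also remains without any benchmark, because no target difference is stated.
- **The entry threshold of 0.3 mm is not a meaningful difference.** It is an eligibility minimum. The protocol gives neither a meaningful difference between designs nor the typical prescribed extrusion. A reader might infer from the comparison with 0.3 mm that the trial cannot detect differences that matter. The documents do not support that: it would need a stated target in mm, and low power is not zero power. The threshold serves only as a scale reference.
- **The repeated-measures spreads may not describe this trial.** Each tooth receives one design and a participant contributes at most two teeth, so nobody supplies all four levels. The 0.68–0.95 mm range is therefore the favourable case, and the independent-groups range should stand beside it.
- **The protocol plans no equivalence conclusion.** That is so. The misreading of a null result is a risk that the sentence invites, not an announced analysis.

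**Conclusion.** The point holds as an error of labelling and inference; the power calculation itself reproduces. The stated 0.199 and 0.146 are f-squared, with f = 0.45 and 0.38 on the error SD or 0.32 and 0.27 on the full SD. They are not small on either scale, and the claim about clinically meaningful differences has no other basis in the protocol.

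In millimetres, 80% power at 20 per group corresponds to a best-to-worst spread of about 0.68–0.95 under the stated model, or 0.95–1.34 with independent groups. These figures assume that the SD of 1.25 is in mm. The first range also assumes ρ = 0.5 and four measurements per unit. The second assumes 20 independent teeth per group, and so ignores any correlation between two teeth of one patient.

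Whether such spreads are too wide to be useful cannot be judged from the documents.

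**What to change.** In Study Population, question 3:

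1. Delete the word *small* and the conclusion drawn from it.
2. State that 0.199 and 0.146 are f-squared, and give f with the SD used for scaling.
3. State the unit of the SD. If it is mm, give the detectable best-to-worst spread at 20 per group as about 0.68–0.95 mm under the repeated-measures model with ρ = 0.5 (0.79–1.12 mm at n = 15). Beside it give about 0.95–1.34 mm for independent groups, noting that this is closer to the tooth-level randomization.
4. State that differences between designs will be reported with confidence intervals, and that a non-significant result will not be read as equivalence.

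A claim about clinically meaningful differences can return only if the investigators state such a difference in mm and compare the detectable spread with it.

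The cost is a few sentences. The stated sensitivity becomes less favourable. No extra patients are needed.

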- No recruitment materials**

4. * Describe the study procedures/methods for identifying and recruiting participants. Address the following three aspects of recruitment in your response.

- 1. Identification of potentially eligible participants or secondary data/specimens of interest.**
- What database(s) will be queried to identify secondary data/specimens

- How potential participants' contact information will be obtained

2. Recruitment procedures to invite participation in the study (when applicable):

- How each of the written or verbal recruitment materials and reminders (selected above) will be used
- Who will contact or respond to potential participants
- Locations where recruitment procedures will take place
- The timing and frequency of recruitment attempts

3. Eligibility screening prior to consent and how those activities will be carried out (when applicable)

See the help text for additional guidance.

1. Patients in this study will be recruited from:

- a. Department of Orthodontics at Virginia Commonwealth University using axiUm, the electronic health record
- b. Two private practice offices (Richmond and Chantilly) in Virginia. These practices own and manage their EHR which will be used to identify potential study participants. Both private practice orthodontists are rated as VIP Diamond plus providers by Invisalign (meaning they are among the top providers of this treatment nationwide) and one of them is also an adjunct faculty who supervises most of the aligner cases treated at VCU.

2. Since the potential participants are those who actively seek orthodontic treatment at any one of these three locations, we would have the contact information and no additional recruitment methods would be used.

3.

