6. * Since a separate protocol document is not uploaded, describe the proposed research using language understandable to those IRB committee members whose expertise is not scientific. The description must include:

1. A statement explaining the study design

2. A detailed description of all the procedures that will be followed to carry out the study, preferably in sequential order, and in sufficient detail that the study's methods could be replicated

3. A description of all research measures/tests/interventions that will be used (if applicable)

See the help text for additional guidance

1.

Randomized Controlled Trial.

The biostatistician on the study team ([name]) will generate random sequence in blocks of 4 using a computer.

All study participants will be assigned a unique identifier (4 digit code) generated by the study team based on order of enrollment and the type of attachment. The key that links code to the patient will be stored in the PI's office computer that has restricted access (only to study personnel). The key will be destroyed when the study is completed.

2.

Members of the study team including residents, [name] will have a meeting prior to start of the study to calibrate on the screening criteria to determine eligibility as well as obtaining signatures and maintaining the consent documents. The team will also have a virtual meeting over zoom at least once a month to update on study progress.

All members of the study team will inform [name] when a study participant is recruited to the study through a secure email. [name] will then communicate the randomly assigned attachment design to the treating orthodontist based on the sequence generated by [name]. The treating orthodontist will then put this information as an order to Align Technology for the fabrication of the attachment trays and clear aligners.

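### Site is in neither the stated randomisation nor the only model named; prespecifying it as a fixed effect is a cheap, modest gain in precision, not a correction of bias

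*Combined protocol and SAP*

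**What the plan says.** Study Procedures, question 4, lists three recruiting sites: the university orthodontic department and two private offices in Virginia. It states that "Both private practice orthodontists are rated as VIP Diamond plus providers by Invisalign" and explains this as standing with the leading providers nationally. The same sentence adds that one of the two is adjunct faculty and oversees most aligner cases at the university. The Consent Groups section refers to residents as treating clinicians. The calibration meeting in Study Procedures, question 6, covers eligibility screening and consent paperwork; treatment is not mentioned.

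On allocation, question 6 says the biostatistician "will generate random sequence in blocks of 4 using a computer". Data Confidentiality and Storage, question 9, repeats the block size and speaks of a list given to the study team. Neither names a stratification factor. Question 6 also gives the size and the unit: "Sample size: 80 maxillary lateral incisors with at least 20 teeth per study group" and "Randomization will occur at the level of individual lateral incisor tooth".

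There is no analysis section. The only model appears in Study Population, question 3: "a one-way repeated measures analysis of variance with a 0.05 significance level will have 80% power". It has no term for site or clinician.

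**The concern.** When one blocked list runs across three sites, arm totals are balanced overall but not within each site. If achieved extrusion differs between sites, that difference enters the arm comparisons as extra random error. With 20 teeth per arm there is little precision to spare, and site is already known for every tooth. Naming the term now also avoids a choice made after the data are seen.

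**Working it through.** **Inputs from the documents.** Four arms, 80 teeth, 20 per arm. SD: "the common standard deviation for extrusion was assumed to be 1.25" (variance 1.5625). Correlation: "a between level correlation, ρ , of 0.5". Target: "Increasing the sample size to 20 per group would have power to detect an effect size of 0.146 and variance of means of 0.114".

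**Inputs assumed.** Site split 40/20/20 (university and two practices); independent teeth; 1.25 taken as the within-site SD; δ = university-versus-private difference in SD units. The documents give neither the split nor δ, so a range is shown.

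**1. The plan's own figure.** Effect size = V/(SD²(1 - ρ)); noncentrality = n × 4 × effect size; df = 3 and (n - 1) × 3. For n = 20, 0.114/(1.5625 × 0.5) = 0.146, df 3 and 57, power 80.0%. For n = 15 at effect size 0.199, power is 79.9%. Both stated figures reproduce.

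**2. Imbalance within sites.** In simulated allocations of 20 blocks of 4 over 40/20/20, the largest and smallest arm within a site differ by 4.6, 4.0 and 4.0 teeth on average (90th percentiles 7, 6, 6). These are extremes over four arms and look larger than their effect on any one contrast.

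**3. Effect on a pairwise contrast.** Baseline standard error = 1.25 × √(2/20) = 0.395 mm. Half the teeth are at the university, so the site indicator has variance 0.25 and SD 0.5.
- δ = 0.5 (0.625 mm): added error 0.625 × 0.5 × √(2/20) = 0.099 mm. Total √(0.395² + 0.099²) = 0.407 mm, about 3% more.
- δ = 1 (1.25 mm): added error 0.198 mm. Total 0.442 mm, about 12% more.

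Simulation gives 0.10 and 0.20 mm.

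**4. Net effect of adjusting.** Adjustment removes that added variance and uses two of 80 - 4 = 76 residual degrees of freedom. Relative efficiency = (1 + 0.25δ²) × 74/76.

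| δ (SD) | mm | Relative efficiency | Change |
|---|---|---|---|
| 0 | 0 | 0.974 | -2.6% |
| 0.25 | 0.31 | 0.989 | -1% |
| 0.33 | 0.41 | 1.000 | 0 |
| 0.5 | 0.63 | 1.035 | +3% |
| 0.75 | 0.94 | 1.111 | +11% |
| 1 | 1.25 | 1.217 | +22% |

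Break-even: 0.25δ² = 76/74 - 1 = 0.027, so δ = 0.33. Steps 3 and 4 describe the same variance, (0.099/0.395)² = 0.0625 = 0.25 × 0.5², and must not be counted as two benefits.

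**5. In terms of power.** Here the total SD is held at 1.25 and site explains a share s of the variance, with independent groups. At V = 0.224, where 80 independent teeth give 80.0%, adding site gives 79.9%, 82.1%, 84.3% and 88.7% for s = 0, 0.05, 0.10 and 0.20.

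**6. Both incisors from one patient.** A patient effect already absorbs much of the site difference. If every patient were bilateral, with an assumed within-patient correlation of 0.5, the gain would fall to about +1% at 0.5 SD and +6% at 1 SD.

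**7. Type I error.** In 3,000 simulated trials per setting with no arm effect, rejection rates were 4.6% to 6.0% with or without site in the model, within simulation error of 5%.

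**The case against.** The strongest reply is that the benefit is unknown and may be negative. The plan reports a credential, not a difference in outcome. One private orthodontist supervises most of the university's aligner cases. Aligners at every site are designed through the same manufacturer's software and made by that manufacturer, and wear instructions are common. If sites differ by less than about 0.41 mm, the site term costs precision. This stands, and it limits the point to a cheap improvement. The loss, however, is capped at about 2.6%, while the possible gain is larger. The shared supervision does not cover the second practice.

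It can also be said that the form is silent on site rather than opposed to it, and that some pages were not available for review. That too is fair: the point is that site is not stated, not that it was rejected.

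A third reply is that site, being constant within a patient, drops out of the within-subject comparison of a true repeated-measures ANOVA (error df 57, not 76). This is correct for that model. But teeth are randomised singly and a patient has at most two lateral incisors, so no patient can receive all four designs. That mismatch is a separate and larger problem: treated as independent groups, 80 teeth give about 48% power at V = 0.114. A site term does not close that gap.

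A reader might infer that the plan itself shows a strong provider effect, or that omitting site biases the comparison of designs. The documents support neither. They give no between-site figure, and randomisation keeps the test valid without site.

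**Conclusion.** The point holds as a modest, inexpensive improvement. Three sites with different operators share a blocked sequence with no stated stratification, and the only named model has no site term. The consequence is some avoidable variance and exposure to chance imbalance. Its size rests on the assumed 40/20/20 split, independent teeth and an unknown site difference: from a 2.6% loss to a 22% gain in efficiency over 0 to 1 SD, and less when bilateral patients are common and a patient effect is fitted. The shared supervision makes the upper end less likely.

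**What to change.** Prespecify the primary model with attachment design and site (three levels) as fixed effects and a random intercept for patient to handle bilateral cases. This can be done whether or not enrolment has begun and needs no new data. The cost is one line of analysis text, two residual degrees of freedom and, if sites do not differ, up to about 2.6% on the variance scale (√(76/74) = 1.013, or 1.3% in standard error).

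Optionally, if enrolment has not started, give each site its own computer-generated list with block sizes varying between 4 and 8; fixed blocks of 4 within a site would make assignments easier to guess. The downside is that arm totals may miss the planned 20. In simulation with an assumed 50/25/25 split, some arm fell below 20 in 87% of trials, typically to 19 or 18. The target of at least 20 per group would then need a small allowance. The model term does not depend on this step.
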